## 5.1.3 Inclusion/Exclusion

The study specific Inclusion/Exclusion Criteria are presented in Section 9.2 and 9.3 of the Clinical Study Protocol.

For each criterion, as appropriate, a response of “Yes/No” is to be obtained at Screening and checked again prior to the first IMP administration, at visit A1.

The following statistical output will be provided:

Listing 16.2.1.3.3 Inclusion Criteria Not Met and Exclusion Criteria Met – Enrolled Set

Listing of inclusion criteria which were not met and exclusion criteria which were met will be presented per patient.

## 5.2 Demographic and Other Baseline Characteristics

### 5.2.1 Demographics

The following demographic characteristics will be presented:

- Age (years)
- Gender (Male, Female)
- Race (White, Black or African American, Asian, American Indian or Alaska Native, Native Hawaiian or Other Pacific Islander, Unknown)
- Women of childbearing potential (Yes, No)

Also, the following physical characteristics at baseline will be presented:

- Height (cm)
- Weight (kg)
- Body mass index BMI (kg/m^2)

Body mass index (BMI) will be calculated as follows:

$$BMI \text{ at Visit } X \text{ (kg/m}^2\text{)} = \frac{\text{Body weight at Visit } X \text{ (kg)}}{[\text{Body height at Visit } 1 \text{ (m)}]^2}$$

The following statistical output will be provided:

Table 15.1.6.1.1 Demographics – Safety Set

Table 15.1.6.1.2 Demographics – Full Analysis Set

Table 15.1.6.1.3 Demographics – Pharmacokinetic Analysis Set

Demographic data will be summarised by HTD and overall in the respective set. Percentage for categorical variables will be based on the respective set.

Table 15.1.6.2.1 Baseline Characteristics – Safety Set

Table 15.1.6.2.2 Baseline Characteristics – Full Analysis Set

Table 15.1.6.2.3 Baseline Characteristics – Pharmacokinetic Analysis Set

Weight, height and BMI data will be summarised by HTD and overall in the respective set.

Listing 16.2.1.5 Demographics and Baseline Characteristics – Enrolled Set

Demographic and baseline characteristic data will be listed for the patients in the enrolled set.

### 5.2.2 Disease Characteristics

The following information on patient PAH status at baseline will be presented:

- WHO functional class at baseline (see Section 5.5.5)
- The cause of PAH:
  - Idiopathic, in non-vasoreactive patients
  - Heritable: Bone morphogenetic protein receptor type II (BMPR2) mutation and other mutations, in non-vasoreactive patients
  - Drugs and toxin induced, in non-vasoreactive patients
  - Associated with connective tissue disease
  - Associated with simple congenital defects (atrial septal defect and/or ventricular septal defect) if closed > 12 months before inclusion
- Does the patient suffer from scleroderma? (yes, no)

The following statistical output will be provided:

Table 15.1.6.3.1 Disease Characteristics – Safety Set

Table 15.1.6.3.2 Disease Characteristics – Full Analysis Set

Table 15.1.6.3.3 Disease Characteristics – Pharmacokinetic Analysis Set

Disease characteristics data will be presented by HTD and overall in the respective set. Percentage for categorical variables will be based on the number of patients in the respective analysis set.

Listing 16.2.1.6 Disease Characteristics – Enrolled Set

Disease characteristics data will be listed for the patients in the enrolled set.

### 5.2.3 Medical History

Medical history encompasses relevant prior or ongoing relevant diseases, conditions, hospitalisation and surgical procedures. Medical history records are collected at Visit 1.

Medical history of the patients includes:

- Medical condition/procedure
- Start date
- Stop date
- Ongoing
- Treatment used (yes, no)

Medical history is classified as:

- **Prior medical conditions** are the conditions which started and ended prior to Visit 1.
- **Ongoing medical conditions** are the conditions which are marked as ongoing at Visit 1 or with a stop date at or after Visit 1

In case of partial missing stop dates, a disease will be considered as ongoing at Visit 1, unless the partial date information clearly indicates that the condition stopped prior to Visit 1.

The following statistical output will be provided:

Table 15.1.7.1.1 Prior Medical Conditions – Safety Set

Table 15.1.7.1.2 Prior Medical Conditions – Full Analysis Set

Table 15.1.7.1.3 Prior Medical Conditions – Pharmacokinetic Analysis Set

Table 15.1.7.2.1 Ongoing Medical Conditions – Safety Set

Table 15.1.7.2.2 Ongoing Medical Conditions – Full Analysis Set

Table 15.1.7.2.3 Ongoing Medical Conditions – Pharmacokinetic Analysis Set

Medical history will be summarised displaying counts and percentages of patients having at least one medical condition and will be presented by Primary System Organ Class (SOC) and by Preferred Term (PT) within SOC. SOC and PT within SOC are to be sorted by descending order of overall incidence. Patients with two or more occurrences of the same condition (as qualified by its PTs) will be counted only once for the respective PT. Percentage will be based on the number of patients in the corresponding analysis set.

Listing 16.2.1.7 Medical History – Enrolled Set

Medical history conditions will be listed for the patients from the enrolled set

### 5.3 Prior and Concomitant Medications

Prior and concomitant medications and therapies are documented in the eCRF.

The following information is collected:

- Medication / therapy
- Indication (Medical history condition, Adverse event, Other)
- Total daily dose
- Units
- Route

- Frequency
- Start date of medication
- Stop date of medication
- Ongoing (yes, no)

Medications and therapies will be classified as ‘prior’, ‘concomitant’ or ‘post-treatment’ based on start/stop dates:

- **Prior medications/therapies** are defined as those medications/therapies starting and ending prior to the first IMP intake.
- **Concomitant medications/therapies** are defined as medications/therapies started at or after first IMP intake and include medications/therapies started prior to the first IMP intake but continued during the study.
- **Post-treatment medications/therapies** are defined as medications/therapies which started after the last IMP intake.

If the start or stop date of a medication/therapy is incomplete or missing, it will be assumed to be concomitant except if the incomplete start or stop date indicates that the medication/therapy started and ended prior to the first IMP intake or started after the last IMP intake.

**PAH medications** will be defined as medications where the preferred term for the indication is “pulmonary arterial hypertension”, “congenital pulmonary hypertension”, or “pulmonary hypertension”, as well as any other medications taken for a condition related to PAH. These medications were selected manually during the Data Review (see Data Review Report, Final 1.0, 10-MAR-2022).

In addition, **PAH-approved** medications will be defined as those medications described in the protocol as being an approved PAH therapy (Ambrisentan, Bosentan, Macitentan, Riociguat, Selexipag, Sildenafil, Tadalafil, Epoprostenol intravenous, Iloprost inhaled or Treprostinil intravenous or subcutaneous) and diuretics. PAH-approved medications were selected manually during the Data Review (see Data Review Report, Final 1.0, 10-MAR-2022).

PAH-approved medications will be combined into groups of monotherapy, double therapy, triple therapy, etc., based on the number of PAH-approved medications taken at a given timepoint.

Concomitant medications will be assigned to IMP dose groups based on the prescribed IMP dose at the time of medication intake. If the start or end date indicates that the medication was taken concurrently with multiple doses, it will be assigned to every corresponding dose. If the start or end date is incomplete such that it could belong to more than one dose, the concomitant medication will be assigned to all such doses.

The following statistical output will be provided:

Table 15.1.8.1.1 Prior Medications – Safety Set

Table 15.1.8.1.2 Prior Medications – Full Analysis Set

Table 15.1.8.1.3 Prior Medications – Pharmacokinetic Analysis Set

Table 15.1.8.2.1 Concomitant Medications – Safety Set

Table 15.1.8.2.2 Concomitant Medications – Full Analysis Set

Table 15.1.8.2.3 Concomitant Medications – Pharmacokinetic Analysis Set

The number and percentage of patients with at least one medication within each ATC 2nd level subgroup. Substance name (or combination of substances) will be presented by HTD for prior medication, by dose for concomitant medications and overall in the corresponding analysis set. The ATC 2nd level subgroups and substance drug name within ATC 2nd level subgroup will be ordered by descending overall incidence. Medications that differ at the substance drug name level but belong to the same therapeutic category will be combined.

Table 15.1.8.3.1 Prior PAH Medications – Safety Set

Table 15.1.8.3.2 Prior PAH Medications – Full Analysis Set

Table 15.1.8.3.3 Prior PAH Medications – Pharmacokinetic Analysis Set

Table 15.1.8.4.1 Concomitant PAH Medications – Safety Set

Table 15.1.8.4.2 Concomitant PAH Medications – Full Analysis Set

Table 15.1.8.4.3 Concomitant PAH Medications – Pharmacokinetic Analysis Set

Medications for pulmonary arterial hypertension will be summarised as above.

Table 15.1.8.5.1 PAH-Approved Therapy by Visit – Safety Set

Table 15.1.8.5.2 PAH-Approved Therapy by Visit – Full Analysis Set

Table 15.1.8.5.3 PAH-Approved Therapy by Visit – Pharmacokinetic Analysis Set

The number and percentage of patients with PAH-approved monotherapy, double therapy, and triple therapy will be summarised at visits A1 and MPV3. The substance names for each therapy combination will be presented by HTD and overall in the corresponding analysis set.

Listing 16.2.1.8 Medications and Therapies – Enrolled Set

All medications, prior, concomitant and subsequent, will be listed for the patients from the enrolled set.

## 5.4 Exposure to IMP and Compliance

### 5.4.1 Exposure to IMP

Exposure data from the eCRF include:

- First IMP intake
- Last IMP intake before the visit (except unscheduled visits)
- IMP intake at the site (except unscheduled visits)
- Last IMP intake (for withdrawals and patients that do not participate in the extension study)
- Date of IMP down-titration

The overall treatment duration in days will be calculated as follows:

$$\text{Overall treatment duration (days)} = \text{last IMP intake date} - \text{first IMP intake date} + 1$$

The following definitions will be used to calculate the overall treatment duration:

- **The date of the first IMP intake** is the date of the IMP intake as recorded at visit A1.
- **The date of the last IMP intake** depends on the patient's decision to participate in the extension study. If the patient is not participating in the extension study, then the last IMP intake is the date of the last intake recorded at the study termination page. If the patient is participating in the extension study, then the on-site IMP intake at MPV3 will be the date of the last IMP intake.

The duration of the study periods in days will be calculated as follows:

$$\begin{aligned} \text{Treatment period duration (days)} \\ = \text{treatment period end date} - \text{treatment period start date} + 1 \end{aligned}$$

See Section 4.6 for definitions of study periods.

Overall and by-period treatment duration will be adjusted in the case of occurrence of adverse events with associated IMP interruption periods. The calendar days between and including start and stop dates of IMP interruptions will not count towards treatment duration.

The following statistical output will be provided:

Table 15.1.9.1.1 Treatment Duration (days) – Safety Set

Table 15.1.9.1.2 Treatment Duration (days) – Full Analysis Set

Table 15.1.9.1.3 Treatment Duration (days) – Pharmacokinetic Analysis Set

The default summary statistics of treatment duration will be presented by HTD and overall.

## 5.4.2 Compliance

The following compliance-related data will be collected in the eCRF:

- date of IMP dispensation
- prescribed IMP dose
- number of tablets dispensed
- dispensed IMP bottle number
- toleration of IMP dose (Yes, No)
- date of IMP down-titration
- date of IMP return
- number of tablets returned
- returned IMP bottle number

The calculation of the compliance will be based on the total number of tablets prescribed, dispensed and returned overall or during particular study period (for definitions of study periods, see Section 4.6).

The total number of tablets prescribed will be calculated as the prescribed daily number of tablets based on the dose (see Section 2.5) multiplied by the length of the dose prescription in calendar days. The total number of prescribed tablets will be adjusted in the case of occurrence of adverse events with associated IMP interruption periods.

The total number of tablets dispensed and returned will be calculated as the sum of all tablets dispensed and all tablets returned during the corresponding study period. The total number of tablets returned will be considered as missing if not all dispensed bottles are returned in the same corresponding period or the returned bottle(s) is from the previous period.

The overall compliance and compliance during each treatment period will be calculated as:

$$\text{Compliance (\%)} = \frac{100 \times (\text{tablets dispensed} - \text{tablets returned})}{\text{tablets prescribed}}$$

In case an IMP bottle is not returned, the overall compliance will be considered as missing.

The following statistical output will be provided:

Table 15.1.9.2.1 Compliance (%) – Safety Set

Table 15.1.9.2.2 Compliance (%) – Full Analysis Set

Table 15.1.9.2.3 Compliance (%) – Pharmacokinetic Analysis Set

The default summary statistics of compliance will be presented by HTD and overall for the respective analysis set. Number and percentage of patients will also be summarised by compliance categories (< 90%, ≥ 90% and ≤ 110%, >110%) for the respective analysis set.

Listing 16.2.2.1 Drug Accountability – Safety Set

Information related drug accountability will be listed for the patients from the safety set.

Listing 16.2.2.2 Exposure to IMP and Compliance – Safety Set

Information related exposure to IMP and compliance will be listed for the patients from the safety set.

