Urinalysis	●			●	●		●		●
Physical examination	●			●	●	●	●		
12-lead electrocardiogram	●	● 		●	●	●	● 		●
Number of digital scars 	●			●	●	●	●		
Modified Rodnan Skin Score 	●						●		
Blood pregnancy test 	●								
Urine pregnancy test 		●		●	●	●	●		●
Arterial blood gas analysis 		●					● 		
Efficacy									
SF-36v2	●						● 		
6-min walk test/Borg dyspnoea score	● 						● 		
Echocardiography	●						● 		
Right heart catheterisation 		●					● 		
Blood withdrawal biomarker	●						● 		

1. EDV = early discontinuation visit. An EDV has to be performed within 10 days of early discontinuation. Additionally, patients who will not participate in the extension study will be contacted by phone at the time of last patient's last visit (LPLV) to document their vital status.

2. Patients will be hospitalised for 24 hours.

3. The dose will be increased if the previous dose was considered safe by the investigator according to safety criteria (at A3, B3 and C3).
4. Blood samples for PK and PD to be taken prior to IMP intake as well as 1, 2, 4, 8, 16 and 24 hours after IMP intake (but still prior to next IMP intake).
5. The patient has to be advised not to take the IMP at home on the day of A3, B3, C3, D3, MPV1, MPV2 and MPV3.
6. Only in women of childbearing potential.
7. Only applicable in patients taking 150 mg or 200 mg zamicastat and who will not participate in the extension study. In case a patient will discontinue the study early due to the occurrence of an AE, down-titration is not mandatory, but at the investigator's discretion.
8. Not applicable at EDV.
9. Visits during the Dose-finding period:
  - Dose A (50 mg zamicastat):** visits A1, A2 and A3
  - Dose B (100 mg zamicastat):** visits B2 and B3. These visits will only be performed if the patient was up-titrated to 100 mg zamicastat at A3.
  - Dose C (150 mg zamicastat):** C2 and C3. These visits will only be performed if the patient was up-titrated to 150 mg zamicastat at B3.
  - Dose D (200 mg zamicastat):** D2 and D3. These visits will only be performed if the patient was up-titrated to 200 mg zamicastat at C3.If the patient's next dose will not be tolerated, the patient will be asked to come to an unscheduled visit (UV) and he/she will be down-titrated to his/her previous dose.

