#### 2.1.2 Secondary Objectives

The secondary objectives of this study are:

1. To assess further PK parameters including apparent total clearance, terminal half-life and apparent volume of distribution \*
2. To assess the safety and tolerability of different zamicastat doses
3. To investigate the effect of different zamicastat doses on plasma dopamine  $\beta$  hydroxylase (D $\beta$ H) activity\*
4. To investigate the effect of different zamicastat doses on urinary catecholamine levels (norepinephrine and dopamine)\*
5. To investigate the change in pulmonary haemodynamic parameters
6. To investigate the change in the 6-minute walk test (6-MWT)
7. To investigate the change in biomarkers
8. To investigate the change in cardiac structure and contractibility, assessed by echocardiography
9. To investigate the change in quality of life, assessed by SF-36v2

\* Covered in a reporting and analysis plan prepared by Quotient Sciences Ltd. (Appendix 4).

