#### Table 15.1.4 Patient Disposition – Safety Set

Counts and percentages of patients who completed the treatment period as scheduled, withdrawals during the treatment period will be summarised by HTD and overall. Reasons associated with the termination will be included. Percentage will be based on the number of patients in the safety set.

Table 15.1.5.1.1 Number of Patients by Country and Site – Enrolled Set

Table 15.1.5.1.2 Number of Patients by Country and Site – Safety Set

Counts and percentages of patients will be presented by country and by site. Percentage will be based on the number of patients in the specified set.

Table 15.1.5.2 Number of Patients by Visit – Safety Set

Counts and percentages of patients who continue the study will be presented by visit. Percentage will be based on the number of patients in the safety set.

Listing 16.2.1.1.1 Patient Disposition – Safety Set

Patients who enter the treatment period and complete the study as scheduled or as withdrawals will be listed. Reasons for premature study termination will be displayed for withdrawals.

Listing 16.2.1.1.2 Screening Failures – Enrolled Set

Patients who discontinued the study during the screening phase prior to enrolment to the treatment period will be listed. Reasons associated with the discontinuation will be displayed.

Listing 16.2.1.2 Patient Visits – Enrolled Set

All visit dates will be listed by patient.

Listing 16.2.1.4 Exclusions from Analysis Sets – Enrolled Set

Patients excluded from any analysis set and corresponding reasons for exclusion will be listed.

Figure 15.1.1 Flow Chart of Patient Disposition – Enrolled Set

Number of patients will be displayed in flow chart by their disposition.

Figure 15.1.2 Flow Chart of Analysis Sets – Enrolled Set

Number of patients will be displayed in flow chart by analysis sets.

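### No described table summarises whether each dose was tolerated, and the by-dose down-titration and discontinuation percentages use the whole safety set instead of the patients who started the dose

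*SAP*

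**What the plan says.** Secondary objective 2 is framed by dose: "To assess the safety and tolerability of different zamicastat doses" (SAP 2.1.2; the same in Protocol 7.2).

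SAP 5.4.2 lists "toleration of IMP dose (Yes, No") and the date of down-titration among the compliance-related eCRF data. Protocol 11.7 also requires the reason for down-titration in the eCRF. The tables attached to SAP 5.4.2 concern compliance alone: "The default summary statistics of compliance will be presented by HTD and overall for the respective analysis set". A patient-level listing might carry the toleration item, but its content is not itemised: "Information related exposure to IMP and compliance will be listed for the patients from the safety set".

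The outputs closest to a tolerability summary are these:

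- **Table 15.1.4 (disposition):** "Counts and percentages of patients who completed the treatment period as scheduled, withdrawals during the treatment period will be summarised by HTD and overall", with reasons for termination.
- **Table 15.1.5.2 (patients by visit):** "Counts and percentages of patients who continue the study will be presented by visit". The B, C and D visits depend on up-titration. For dose B the schedule in SAP 1.2 says: "These visits will only be performed if the patient was up-titrated to 100 mg zamicastat at A3".
- **Tables 15.3.1.7 and 15.3.1.8:** treatment-emergent adverse events (TEAEs) leading to down-titration and to discontinuation, by concurrent dose, with patient counts. SAP 5.6.1 bases the percentages of Tables 15.3.1.2 to 15.3.1.9 on the safety set. SAP 4.3 adds that adverse events are summarised by concurrent dose without placing patients in dose groups.

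**The concern.** In a study built on individual titration, the plainest description of tolerability is, for each dose, how many patients started it, how many tolerated it, how many were taken down from it and how many withdrew while on it. The item that answers the second question is collected and then feeds no described table. The remaining counts are spread over outputs with different groupings (HTD, visit, concurrent dose), and the by-dose percentages have a denominator that includes patients who never took the dose.

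At stake is how objective 2 reads in the study report. The bias runs one way: towards fewer apparent problems at the higher doses.

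**Working it through.** The plan states no figure on this point to reproduce. The 32 patients are not formula-based (SAP 2.6). The check is therefore a comparison of outputs, followed by an illustration of the denominator effect.

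**1. What each planned output gives for a single dose**

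| Count wanted per dose | Nearest planned output | What is missing |
|---|---|---|
| Started | Table 15.1.5.2, through the B, C and D visits | Approximate. Each new dose starts at A3, B3 or C3, and the next scheduled contact is 8 ± 2 days later. A patient down-titrated before then may have no visit under that dose. |
| Tolerated Yes/No | None described; HTD column sizes are a proxy | The recorded item itself |
| Down-titrated | Table 15.3.1.7 | TEAEs with the action recorded as dose reduced, on a safety-set denominator |
| Withdrawn | Table 15.1.4 by HTD; Table 15.3.1.8 for TEAEs | All-reason withdrawals by the dose being taken |

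**2. The HTD columns**

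SAP 2.3 defines the HTD as the dose taken in the maintenance period. SAP 4.3 reserves the No HTD group for patients who do not tolerate 50 mg. A patient who withdraws consent, or is withdrawn, during dose finding on 100, 150 or 200 mg has no maintenance dose and did not fail 50 mg. Neither rule assigns that patient a column in Table 15.1.4.

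**3. The denominator**

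Every treated patient starts at 50 mg, so the safety set is the right denominator for that dose. Above 50 mg, let x be the patients with the event, S the number who started the dose and N the safety set:

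- printed percentage = x / N
- rate among those exposed = x / S
- ratio of printed to exposed = S / N, which is below 1 whenever some patients did not start the dose.

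The documents give no counts by dose. Assume N = 32 (the planned size), x = 4 or 2, and S between 16 and 24. Intervals are exact (Clopper-Pearson) 95%.

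| Denominator | x = 4 | 95% CI | x = 2 |
|---|---|---|---|
| 32 (safety set) | 12.5% | 3.5 to 29.0 | 6.25% |
| 24 started | 16.7% | 4.7 to 37.4 | 8.3% |
| 20 started | 20.0% | 5.7 to 43.7 | 10.0% |
| 16 started | 25.0% | 7.3 to 52.4 | 12.5% |

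The printed percentage is 16/32 = 0.50 to 24/32 = 0.75 of the rate among starters.

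The comparison between doses is distorted too. Suppose the rate is 25% both at a dose that 24 patients started (6 events) and at a higher dose that 16 started (4 events). The tables would print 6/32 = 18.75% and 4/32 = 12.5%, an apparent fall with dose where there is none.

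**The case against.** Much of the content is planned, and several stronger readings do not survive.

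- **A reader might infer that down-titration and withdrawal have no table.** They do: Tables 15.3.1.7 and 15.3.1.8 count patients by concurrent dose, and Table 15.1.4 gives withdrawals with reasons by HTD. Maintenance begins only at D3 or at down-titration, so an HTD of 50, 100 or 150 mg itself shows a step back from the next dose.
- **A reader might infer that a blood pressure or ECG criterion failed without an adverse event goes uncounted.** Protocol 12.1.1 makes such an abnormality recordable as an adverse event if it is clinically significant or changes the patient's study schedule, among other conditions. Most findings that force a down-titration should therefore reach Table 15.3.1.7.
- **A reader might infer that tolerability by dose cannot be reported.** The data exist. SAP 4.6 defines a toleration period for each dose, and SAP 5.4.1 derives durations by period. The plan simply does not say that these are shown dose by dose.
- **No declared endpoint is missing.** The safety and tolerability endpoints in Protocol 13.1.2.1 do not include a per-dose toleration rate.
- **The shells listed in SAP section 10 are not in the available text.** A toleration row could sit inside an existing table or in the disposition flow chart.

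All of this stands, and it narrows the point. It does not answer the two problems created by the stated rules: the safety-set denominator for by-dose percentages, and the undefined HTD column for patients withdrawn during dose finding above 50 mg.

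**Conclusion.** The point holds in a limited form. The SAP text describes no table of the toleration item. Withdrawals for all reasons are grouped by an HTD that is undefined for some patients, and by-dose TEAE percentages are understated by the factor S/N at any dose not started by everyone. In the assumed range of 16 to 24 starters out of 32, a printed 12.5% stands for 16.7% to 25.0% among those exposed. The size in this study depends on how many patients reached each dose, which the documents do not give.

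This is a reporting gap in an exploratory, descriptive study, and it should be corrected because following the written rules yields misleading percentages. A reader might extend it to the primary aim of finding a dose range. The documents do not support that: the primary objective is evaluated through pharmacokinetics, and SAP 2.1.1 places that analysis outside this SAP. The conclusion assumes that the unseen shells follow the SAP text.

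**What to change.** Add one safety-set table with a column for each dose (50, 100, 150 and 200 mg), counting each patient once per dose started:

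- N who started the dose;
- n who completed the dose period;
- n recorded as tolerating the dose, Yes and No;
- n down-titrated from the dose, for any reason, with the reasons;
- n withdrawn while on the dose, for any reason, with the reasons.

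Base percentages on N started; exact 95% intervals are optional. Use the same N-started denominator in the by-dose columns of Tables 15.3.1.1 to 15.3.1.9, and keep the safety set for the overall column. State in SAP 4.3 where Table 15.1.4 shows patients withdrawn during dose finding above 50 mg.

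The cost is a little extra programming on data already collected, with no change to study conduct. If the shells already contain such a table on the right denominator, a cross-reference in the SAP is enough.
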